5.2 EXCLUSION CRITERIA

An individual who meets any of the following criteria will be excluded from participation in this study:

1. Patients with a second active malignancy, exceptions are localized non-melanoma skin cancers or in situ carcinoma
2. Patients receiving any other investigational agents
3. Participants with tumor(s) in direct contact or encasing a major blood vessel, those with ulceration and/or fungation onto the skin surface, and those with history of re-irradiation or prior lymph node neck dissection to a field involving the carotid arteries
4. History or evidence of active autoimmune disease that requires systemic treatment (ie, with use of disease modifying agents, corticosteroids or immunosuppressive drugs). Replacement therapy (eg, thyroxine, insulin, or physiologic corticosteroid replacement therapy for adrenal or pituitary insufficiency, etc.) is not considered a form of systemic treatment.
5. Evidence of clinically significant immunosuppression such as the following:
 - a. - Primary immunodeficiency state such as Severe Combined Immunodeficiency Disease.
 - b. - concurrent opportunistic infection.
 - c. - receiving systemic immunosuppressive therapy (> 2 weeks) including oral steroid doses > 10 mg/day of prednisone or equivalent within 7 days prior to enrollment.
6. Active herpetic skin lesions or prior complications of HSV-1 infection (e.g., herpetic keratitis or encephalitis).
7. Requires intermittent or chronic systemic (intravenous or oral) treatment with an antiherpetic drug (e.g., acyclovir), other than intermittent topical use.
8. Previous treatment with talimogene laherparepvec or any other oncolytic virus.
9. Prior therapy with tumor vaccine.
10. Received live vaccine within 28 days prior to enrollment.
11. Prior immunosuppressive, chemotherapy, radiotherapy (in which the field encompassed a planned injection site), biological cancer therapy, or major surgery within 28 days prior to enrollment or has not recovered to CTCAE grade 1 or better from adverse event due to cancer therapy administered more than 28 days prior to enrollment.
12. Prior radiotherapy in which the field does not overlap the injection sites or non-immunosuppressive targeted therapy within 14 days prior to enrollment or has not recovered to CTCAE grade 1 or better from adverse event due to cancer therapy administered more than 14 days prior to enrollment
13. Currently receiving treatment with another investigational device or drug study, or < 28 days since ending treatment with another investigational device or drug study(s).
14. Other investigational procedures while participating in this study are excluded.
15. Known to have acute or chronic active hepatitis B infection, hepatitis C infection, or human immunodeficiency virus (HIV) infection.
16. History of other malignancy within the past 5 years with the following exceptions: adequately treated non melanoma skin cancer, cervical carcinoma in situ, breast ductal carcinoma in situ, or prostatic intraepithelial neoplasia without evidence of disease at the time of enrollment
17. Subject has known sensitivity to talimogene laherparepvec or any of its components to be administered during dosing.
18. Female subject is pregnant or breast-feeding, or planning to become pregnant during study treatment and through 3 months after the last dose of talimogene laherparepvec.
19. Female subject of childbearing potential who is unwilling to use acceptable method(s) of effective contraception during study treatment and through 3 months after the last dose of talimogene laherparepvec.

20. Sexually active subjects and their partners unwilling to use male or female latex condom to avoid potential viral transmission during sexual contact while on treatment and within 30 days after treatment with talimogene laherparepvec.
21. Subjects who are unwilling to minimize exposure with his/her blood or other body fluids to individuals who are at higher risks for HSV-1 induced complications such as immunosuppressed individuals, individuals known to have HIV infection, pregnant women, or infants under the age of 3 months, during talimogene laherparepvec treatment and through 30 days after the last dose of talimogene laherparepvec.

5.3 LIFESTYLE CONSIDERATIONS

- Female subjects cannot be pregnant or breast-feeding, or planning to become pregnant during study treatment and through 3 months after the last dose of talimogene laherparepvec.
- Female subject of childbearing potential must use acceptable method(s) of effective contraception during study treatment and through 3 months after the last dose of talimogene laherparepvec.
- Sexually active subjects and their partners must use male or female latex condom to avoid potential viral transmission during sexual contact while on treatment and within 30 days after treatment with talimogene laherparepvec.
- Subjects must minimize exposure with his/her blood or other body fluids to individuals who are at higher risks for HSV-1 induced complications such as immunosuppressed individuals, individuals known to have HIV infection, pregnant women, or infants under the age of 3 months, during talimogene laherparepvec treatment and through 30 days after the last dose of talimogene laherparepvec.
- Participants who use tobacco products will be instructed that use of nicotine-containing products (including nicotine patches) will not be permitted while they are in the clinical unit.
- Abstain from strenuous exercise for 12 hours before each blood collection for clinical laboratory tests. Participants may participate in light recreational activities during studies (e.g., watching television, reading).

5.4 SCREEN FAILURES

Screen failures are defined as participants who consent to participate in the clinical trial but do subsequently receive the study intervention or entered in the study. A minimal set of screen failure information is required to ensure transparent reporting of screen failure participants, to meet the Consolidated Standards of Reporting Trials (CONSORT) publishing requirements and to respond to queries from regulatory authorities. Minimal information includes demography, screen failure details, eligibility criteria, and any serious adverse event (SAE).

Individuals who do not meet the criteria for participation in this trial (screen failure) because of a poor performance status may be rescreened. Rescreened participants should be assigned the same participant number as for the initial screening.

5.5 STRATEGIES FOR RECRUITMENT AND RETENTION

Both men and women and members of all races and ethnic groups are eligible for this trial. It is anticipated that one patient per month will be accrued. The source of patients will be from the outpatient clinics and general public. The study will be advertised through patient advocacy groups, social media, and flyers in the clinic to increase participation. Given the participation over one year, we will use multiple methods to contact patients including phone, email, and EHR patient portal to ensure continued participation.

6 STUDY INTERVENTION

6.1 STUDY INTERVENTION(S) ADMINISTRATION

6.1.1 STUDY INTERVENTION DESCRIPTION

This trial will use talimogene laherparepvec (T-VEC) as monotherapy for the treatment of locally advanced, relapsed/refractory cutaneous angiosarcoma. Full details regarding this drug are included in the Investigator Brochure and pharmacy insert (http://pi.amgen.com/~media/amgen/repositorysites/pi-amgen-com/imlytic/imlytic_pi). Treatment will be administered on an outpatient basis. Reported adverse events and potential risks for T-VEC are described in Section 2.3. Appropriate dose modifications for T-VEC are described in Section 6.1.2.3. No investigational or commercial agents or therapies other than those described below may be administered with the intent to treat the patient's malignancy. Standard supportive care medications are allowed.

6.1.2 DOSING AND ADMINISTRATION

6.1.2.1 T-VEC TREATMENT PLAN

The first and second injections of T-VEC will be injected into the tumor 3 weeks apart (+3 days) to allow for seroconversion, and then the remaining injections will be given every 2 weeks (+/- 3 days) directly into the primary tumor only, for up to 1 year of injections.

The 10^6 PFU/mL dose will be used for the initial injection (up to 4 mL total volume), while all subsequent injections will be done with 10^8 PFU/mL (up to 4 mL total volume).

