1 PROTOCOL SUMMARY

1.1 SYNOPSIS

Title: A phase II study of talimogene laherparepvec (T-VEC) in the treatment of recurrent cutaneous angiosarcoma

Study Description: Seventy-five percent of cutaneous angiosarcoma (CA) patients will eventually fail systemic therapy, and relapsed/refractory patients are left with no known efficacious treatment options. We hypothesize that direct treatment of CA lesions with T-VEC will stimulate local antitumor response, leading to objective responses and prevention of recurrence among enough patients to make this a viable treatment option for the affected population.

Objectives:

Primary Objective: To evaluate the efficacy of T-VEC as treatment for relapsed/refractory cutaneous angiosarcoma

Secondary Objectives:

1. To establish duration of response among treated patients that demonstrate response
2. To measure the duration of progression-free survival among treated patients
3. To measure the complete response rate for lesions that have complete clinical regression following study treatment
4. To monitor adverse events following administration of T-VEC injections
5. To measure the rate of patients requiring surgical resection of T-VEC–treated lesions

Tertiary/Exploratory Objectives:

1. To measure the degree of immune infiltration in surgically resected T-VEC–treated tumors
2. To evaluate surgical outcomes for those patients whose T-VEC–treated tumors are resected

Endpoints:

Primary Endpoint: Overall response rate: the proportion of patients to demonstrate complete or partial responses in injected lesions per modified RECIST criteria appropriate for cutaneous neoplasms.

Secondary Endpoints:

1. Response duration will be measured from the time of initial partial response or complete response until documented progression

2. Progression-free survival: period from time of first injection to progression of disease or appearance of new cutaneous angiosarcoma tumors that were not present at the time of study entry
3. Complete Response rate: proportion of patients with CR, defined as lesions with complete clinical regression
4. Incidence of adverse events from injection of T-VEC into cutaneous angiosarcoma
5. Proportion of patients whose T-VEC–treated tumors require surgical resection

Tertiary/Exploratory Endpoints:

1. Immunohistochemistry and flow cytometry analyses of immune infiltration within resected tumor specimens

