2.2 BACKGROUND

2.2.1 DISEASE BACKGROUND

CA is a rare cutaneous neoplasm that is classified as a soft tissue sarcoma which arises within the epidermis or dermis. The disease presents largely as 2 separate phenotypes. In one form, the cause is idiopathic and effects elderly men with a predilection for occurrence in the head and neck region. In another form, the disease is associated with a history of radiation therapy and most commonly affects women, with disease occurring in the skin of the breast after breast conservation therapy for primary breast cancer. The latter form occurs with a median latency period of 7 years between the exposure to radiation and development of a secondary malignancy.

Treatment for either condition is primarily wide surgical resection. Wide margins can be difficult to obtain as anatomic constraints often limit the resection. Even when primary resection is feasible, recurrence is common, with a local recurrence rate up to 60% for those with idiopathic cutaneous angiosarcoma and 75% for those with radiation-associated cutaneous angiosarcoma. Complicating treatment further is the presence of multifocal disease in both the primary and recurrent setting, which is difficult to manage with surgical resection. Despite the known association, radiation therapy has been advocated for cutaneous angiosarcoma as a way to increase local control.

With high local recurrence rates, there is an unmet need for local therapy. The anatomic constraints limiting resection in the primary setting are worse with recurrence and repeat radiation therapy to a site is generally not feasible. Systemic therapy is used for these patients; however, these options are often restricted by the limitations associated with the age of these often elderly patients.

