8 STUDY ASSESSMENTS AND PROCEDURES

8.1 EFFICACY ASSESSMENTS

8.1.1 PRE-STUDY PROCEDURES

To be performed no more 4 weeks prior to initiation of study treatment

Imaging: CT chest, abdomen, and pelvis with IV contrast

To be performed within 1 week of 1st study treatment evaluation

Informed consent, demographics, concomitant medications, performance status, physical examination, vitals, height, weight, complete blood count, complete metabolic panel, serum pregnancy test completed within 72 hours of enrollment, serum HSV1 Ab, electrocardiogram, tumor measurement by palpation/exam, request slides from tumor biopsies for immunohistochemical analysis.

Week 1 procedures:

Complete blood count, complete metabolic panel, pharmacy to begin thawing/preparation of dose, clinic visit with concurrent medications, performance status, physical examination, vitals, weight, tumor measurement by examination, injection of T-VEC into primary tumor.

Weeks 2, 3 and 6:

Clinic visit with concurrent medications, performance status, physical examination, vitals, weight, anti-HSV Ab titer on week 6 only

Bi-weekly procedures starting Week 4-week 52:

Complete blood count, complete metabolic panel, pharmacy to begin thawing/preparation of dose, clinic visit with concurrent medications, performance status, physical examination, vitals, weight, tumor measurement by examination, injection of T-VEC into primary tumor.

Off-study procedures:

Complete blood count, complete metabolic panel, clinic visit with concurrent medications, performance status, physical examination, vitals, weight, and punch biopsy all within 30 days of last study treatment. Follow up of any treatment-related adverse events until resolution, stabilization, or death for a minimum of 30 days after last study treatment. Data on any perioperative complications should be also collected as applicable. Final tumor

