8.1.2.1 DEFINITIONS

Evaluable for toxicity. All patients will be evaluable for toxicity from the time of their first treatment with T-VEC

Evaluable for objective response. Only those patients who have measurable disease present at baseline, have received at least three injections at the 10^8 dose level, and have had their disease re-evaluated will be considered evaluable for response. These patients will have their response classified according to the definitions stated below.

Evaluable Non-Target Disease Response. Patients who have lesions present at baseline that are evaluable but do not meet the definitions of measurable disease, have received at least one cycle of therapy, and have had their disease re-evaluated will be considered evaluable for non-target disease. The response assessment is based on the presence, absence, or unequivocal progression of the lesions.

Disease Parameters

Measurable disease. Measurable lesions are defined as those that can be accurately measured in at least one dimension (longest diameter to be recorded) as ≥ 6 mm by calipers on clinical examination. All tumor measurements must be recorded in millimeters (or decimal fractions of centimeters).

Non-measurable disease. All other lesions (or sites of disease), including small lesions (longest diameter < 6 mm) are considered non-measurable disease.

Note: Cystic lesions that meet the criteria for radiographically defined simple cysts should not be considered as malignant lesions (neither measurable nor non-measurable) since they are, by definition, simple cysts.

“Cystic lesions” thought to represent cystic metastases can be considered as measurable lesions if they meet the definition of measurability described above. However, if non-cystic lesions are present in the same patient, these are preferred for selection as target lesions.

Target lesions. All measurable lesions up to a maximum of 5 lesions in total, representative of all involved organs, should be identified as **target lesions** and recorded and measured at baseline. Target lesions should be selected on the basis of their size (lesions with the longest diameter), but in addition should be those that lend themselves to

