reproducible repeated measurements. It may be the case that, on occasion, the largest lesion does not lend itself to reproducible measurement in which circumstance the next largest lesion that can be measured reproducibly should be selected. A sum of the diameters (longest for non-nodal lesions, short axis for nodal lesions) for all target lesions will be calculated and reported as the baseline sum diameters. The baseline sum diameters will be used as reference to further characterize any objective tumor regression in the measurable dimension of the disease. All target lesions will also be injected lesions.

Non-target lesions. All other lesions (or sites of disease) including any measurable lesions over and above the 5 target lesions should be identified as **non-target lesions** and should also be recorded at baseline. Measurements of these lesions are not required, but the presence, absence, or in rare cases unequivocal progression of each should be noted throughout follow-up. All non-target lesions will not be injected with T-VEC.

Methods for Evaluation of Measurable Disease

All measurements should be taken and recorded in metric notation using a ruler or calipers. All baseline evaluations should be performed as closely as possible to the beginning of treatment and never more than 4 weeks before the beginning of the treatment.

Clinical lesions. Clinical lesions will only be considered measurable when they are superficial (e.g., skin nodules and palpable lymph nodes) and ≥ 6 mm diameter as assessed using calipers. Documentation by color photography at baseline, including a ruler to estimate the size of the lesion, is recommended.

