9.4.2 ANALYSIS OF THE PRIMARY EFFICACY ENDPOINT(S)

Our primary endpoint for this analysis will be confirmed overall response rate (ORR) in injected lesions based on modified RECIST criteria appropriate for cutaneous neoplasms (ORR = complete response + partial response)

According to the Simon's two-stage design, after testing the treatment on 8 patients in the first stage, the trial will be terminated if 1 or fewer responds. If the trial goes on to the second stage, a total of 13 patients will be studied. If the total number responding is less than or equal to 3, the treatment is rejected. Please see Sample Size description above for further details.

In addition, we will construct a 95% exact confidence interval for the ORR.

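### Dosing text (6.1.2.1, 8.1.1) names the primary tumor, while 8.1.2.1 has up to five target lesions all injected and scored; if the dosing text is followed, uninjected lesions enter the response sum

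*Combined protocol and SAP*

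**What the plan says.** Two parts of the current text say which lesions receive drug.

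- **Dosing and visit text.** Section 6.1.2.1 puts the first two doses into the tumor and the remaining ones "directly into the primary tumor only, for up to 1 year of injections". Section 8.1.1 lists "injection of T-VEC into primary tumor" at Week 1 and at each bi-weekly visit from Week 4 to Week 52.
- **Response definitions.** Section 8.1.2.1 takes as targets "All measurable lesions up to a maximum of 5 lesions in total". It then states "All target lesions will also be injected lesions" and "All non-target lesions will not be injected with T-VEC".

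Section 8.1.2.3 scores complete and partial response on the target lesions, with partial response set at a fall of at least 30% in their summed diameters from baseline. The primary endpoint is "complete or partial responses in injected lesions per modified RECIST criteria appropriate for cutaneous neoplasms" in the Synopsis (1.1) and "confirmed overall response rate (ORR) in injected lesions" in 9.4.2.

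Three other places bear on intent. The Synopsis ties the dose to the size of one or more lesions to be injected. Section 6.1.2.2 refers to injectable lesions in the plural and caps a treatment at 4.0 mL in total. Section 6.1.2.3 lets new locoregional disease be injected at the PI's discretion. No section defines primary tumor or says which text governs.

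**The concern.** The primary endpoint is defined by which lesions are injected, yet it is computed on which lesions are targets. The two sets agree only if every target is injected. Section 8.1.2.1 secures that; 6.1.2.1 and 8.1.1, followed literally, do not.

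The case is realistic. Section 2.2.1 describes "the presence of multifocal disease in both the primary and recurrent setting", and the trial enrolls recurrent disease. After an earlier resection it may not be clear which lesion is the primary one.

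The person injecting would look to the dosing section and the visit list, while the person choosing targets would look to 8.1.2.1. If each follows the relevant section, the same shrinkage of the one injected lesion can be a partial response on that lesion and stable disease on the target sum. A complete response cannot be recorded while an uninjected target persists. The decision boundaries lie between 1 and 2 responders of 8 and between 3 and 4 of 13, so one patient classified differently can matter.

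**Working it through.** **1. The plan's own design figures.** Inputs from 9.1 and 9.2: null rate 0.10, alternative 0.40, 8 then 13 patients, stop at 1 or fewer responders, reject the treatment at 3 or fewer.

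- Probability of early termination under the null: 0.9^8 + 8 × 0.1 × 0.9^7 = 0.4305 + 0.3826 = 0.8131 (stated 0.813).
- Expected sample size: 8 + 5 × (1 − 0.8131) = 8.93 (stated 8.93).
- Probability of at least 2 responders in stage 1 and at least 4 in total, exact binomial: 0.0307 at a rate of 0.10 (stated 0.031) and 0.8015 at 0.40, so type II error 0.198 (stated 0.198).

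All four figures reproduce. None depends on which lesions are injected, so the inconsistency leaves them as they are.

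**2. The texts applied to one patient with several measurable lesions.**

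| Question | 6.1.2.1 and 8.1.1 | 8.1.2.1 |
|---|---|---|
| Lesions injected | the primary tumor | every target |
| Lesions summed for response | not addressed | every target, up to five |
| Injected set equals scored set? | only if there is a single target | yes |

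Naming only the injected lesion as the target would restore agreement, but it breaks the rule in 8.1.2.1 that all measurable lesions up to five are targets.

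**3. Effect on scoring (illustration).** Assume k targets of equal diameter and one injected. The injected lesion shrinks by a fraction s and each of the others by u (negative u is growth).

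- Fall in the sum = (s + (k − 1)u) / k.
- Partial response needs s ≥ 0.30k − (k − 1)u, and is impossible when that exceeds 1.

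Shrinkage of the injected lesion needed for a partial response:

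| Uninjected lesions | k = 1 | k = 2 | k = 3 | k = 4 | k = 5 |
|---|---|---|---|---|---|
| Unchanged (u = 0) | 30% | 60% | 90% | impossible | impossible |
| Each shrinks 10% | 30% | 50% | 70% | 90% | impossible |
| Each shrinks 20% | 30% | 40% | 50% | 60% | 70% |
| Each grows 10% | 30% | 70% | impossible | impossible | impossible |

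In the first row, complete disappearance of the injected lesion lowers the sum by 1/k: 25% at k = 4 and 20% at k = 5, both short of 30%. If all k targets are injected and each shrinks by 30%, the sum falls by 30% for every k.

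**4. Does rewording alone align the sets?** The guideline volumes in 6.1.2.2 are maxima by lesion size. One lesion above 5.0 cm takes 4.0 mL; two of more than 2.5 to 5.0 cm take 2 × 2.0 = 4.0 mL; three take 6.0 mL. The first two cases use up the 4.0 mL treatment cap, and any further target could go uninjected at that visit yet still count in the sum. New lesions injected under 6.1.2.3 create the opposite mismatch: injected but not baseline targets. The amendment has to address both.

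**The case against.** The strongest reply is that 8.1.2.1 already prevents the problem. It says that targets are injected and non-targets are not, and the Synopsis, 6.1.2.2 and 6.1.2.3 point the same way. Harm needs a mixed reading, with the target count taken from 8.1.2.1 and its injection rule ignored. The exclusive restriction rests on one clause in 6.1.2.1, covering only injections after the second; 8.1.1 says primary tumor without restricting injection to it.

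The phrase may also be loose or carried over. Section 8.1.1 speaks of neoadjuvant therapy although 5.1 requires that resection be of no benefit, 10.1.5 refers to defining an MTD although there is no dose finding, and 8.3.1 calls the biopsied lesion the primary tumor. This is one center, with injections by privileged staff physicians and weekly group review.

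Much of this stands. Multi-lesion injection is very probably intended, and a reader who infers that the trial deliberately restricts treatment to one lesion goes beyond the documents. The scored set is also settled: 8.1.2.1 and 8.1.2.3 fix it as the baseline targets. But clear intent does not correct an operative dosing instruction that says otherwise, and the mixed reading is what results when each person follows the section written for that task.

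**Conclusion.** An internal inconsistency, wrong as written, that should be fixed. The conflict between 6.1.2.1 with 8.1.1 and 8.1.2.1 follows directly from the text. The consequence is conditional: it arises only in patients with more than one measurable lesion, and only if dosing follows 6.1.2.1 and 8.1.1 while targets are chosen under 8.1.2.1. In that case, with equal lesions, one injected and the others unchanged, the shrinkage required for partial response rises from 30% to 60% and 90% at two and three targets and becomes unattainable at four or five. Those percentages rest on assumed lesion sizes and behavior.

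A reader might infer that the trial will understate the response rate or lose power. The documents do not support that: they give no distribution of lesion number or size and no indication of which text staff would follow, so no effect on ORR or power can be estimated. Sample size, decision rule and stated error rates stand.

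**What to change.** - In 6.1.2.1 and 8.1.1, replace primary tumor (only) with *all target lesions identified at baseline*, subject to the clinical team's confirmation that this is the intent.
- State what happens when guideline volumes exceed the 4.0 mL treatment cap. Either the volume is divided so that every target receives some drug at each treatment, which the guideline permits because its volumes are maxima, or targets are limited at baseline to lesions that can be injected within the cap. The second option also needs a sentence in 8.1.2.1.
- State that new locoregional lesions injected under 6.1.2.3 do not enter the baseline target sum and are still handled as new lesions under 8.1.2.3.
- Record injection by lesion at each visit, so that agreement between injected and scored sets can be checked.

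The cost is a few sentences and one lesion-level CRF field. Sample size, response thresholds and decision rule do not change.
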